9.3. Sample size and power

We are aiming for a target sample size of 150 participants. For a two tailed analysis with α =0.05, $Z\alpha$ = 1.96 and with β =0.2, $Z\beta$ = 0.8, N=120, the study should be powered at 80% to detect a true difference in MADRS scale score between the mangosteen pericarp and placebo groups if the effect size is

Cohen's *d*=0.362 or greater. This is a conservative estimate, based on the results of the pilot data. However, in our previous trial of N-acetylcysteine specifically investigating bipolar depression, effect sizes for depressive symptoms (BDRS, MADRS), clinical global impression of depressive severity (CGI BP-depression), as well as all functional measures have shown effects similar to or above the effect size the sample has been calculated for. Based on our previous trials we typically have an attrition rate of 20%. Therefore, although power calculations indicated 120 participants will be sufficient to detect between group differences, we plan to recruit 150 participants to account for attrition.

10.Ethics

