6.6. Randomisation

After the baseline assessment has been completed, the participant will be randomised to either the *Garcinia mangostana* Linn group or the placebo group. Allocation to treatment arm will be randomly assigned in a 1:1 ratio (active to placebo) using permutated block randomisation. An independent researcher utilising a four-to-a-block design will develop the computer-generated randomisation plan. Trial clinicians will allocate packs sequentially, and bottles are identical so as to conceal treatment allocation and blinding. To facilitate the double-blinding process, the trial medications will be dispensed by an independent pharmacist in identical numbers and capsule forms in sealed containers. The statistician and trial clinicians will be blinded to the group allocation.

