9.2. Method of statistical analysis

All analyses will be conducted in accordance with the International Conference on Harmonization E9 statistical principles, and are based on all randomised participants with at least one post-baseline observation (intention to treat population). Reporting of research findings will be done in accordance to CONSORT guidelines. The statistician responsible for the analysis of outcome data will be blind to group allocation. The primary efficacy analysis will assess average treatment group differences for the primary outcome measure MADRS total score over the entire study period and will use a likelihood based mixed-effects model, repeated measures approach (MMRM). The MMRM model includes the fixed, categorical effects of treatment, investigator, visit, and treatment-by-visit interaction, as well as the continuous, fixed covariates of baseline score and baseline score-by-visit interaction. The MMRM includes all available data at each time point and is the preferred method of analyzing clinical trial data in psychiatry as compared to more traditional repeated measures analysis of variance (ANOVA) and analysis of covariance models (ANCOVA). Planned comparisons will be done with the MMRM models to determine between group differences in change of symptoms measures from baseline to week 24. Results from the analysis of dichotomous data will be presented as proportions, with 95% confidence interval, and Fisher's exact p-value where appropriate. Non-parametric statistics will be used when assumptions for parametric methods are violated. Effect sizes will be calculated using Cohen's guidelines. All tests of treatment effects will be conducted using a two-sided alpha level of 0.05 and 95% confidence intervals. Change scores in symptoms and in biological markers will be derived. Pearson Product Moment Correlations will be used to examine the relationships between the change scores for symptoms and the change scores for biological markers in the two groups. Using Fisher's z transformation, we will test whether the correlations obtained for each group are statistically different in terms of strength.

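### Section 9.3's inputs do not give 80% power at d=0.362: that effect goes with 120 per arm, and the design has 60 evaluable per arm

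*Protocol*

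**What the plan says.** Section 9.3 opens the calculation with "For a two tailed analysis with" alpha 0.05 (Z 1.96) and beta 0.2 (Z printed as 0.8). It concludes that, with "N=120, the study should be powered at 80% to detect a true difference in MADRS scale score" between the two groups if the effect is "Cohen's *d*=0.362 or greater". It adds: "This is a conservative estimate, based on the results of the pilot data".

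The same section shows that 120 counts the whole trial: "although power calculations indicated 120 participants will be sufficient to detect between group differences, we plan to recruit 150 participants", the increase being for an expected attrition of 20%. Sections 5.2 and 5.3 both give 150 as the trial size. Under section 6.6 participants are "randomly assigned in a 1:1 ratio (active to placebo"). Section 9.2 confirms the error rate: "All tests of treatment effects will be conducted using a two-sided alpha level of 0.05".

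The primary analysis in section 9.2 is an MMRM of MADRS total score. It estimates the average treatment difference over the study period, with baseline score and its interaction with visit as covariates. The power statement gives no baseline correlation, no between-visit correlation and no time course of effect.

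**The concern.** The power statement is the only quantitative justification for the sample size. Its four inputs (alpha, power, N and d) are those of a plain comparison of two means, and they can be checked against each other. They are inconsistent: the stated effect belongs to a trial with twice as many evaluable participants.

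What is at stake is what the trial can be said to detect. Section 9.3 also reports that effects in the earlier N-acetylcysteine trial were similar to or above the design effect. If the threshold should be about 0.52 instead of 0.362, that reassurance is measured against the wrong number.

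**Working it through.** **Inputs.** Two-sided alpha 0.05, Z = 1.960 (9.2, 9.3). Power 80%, Z = 0.842 (9.3). d = 0.362 (9.3). Evaluable total 120, recruited 150, attrition 20% (9.3): 120/0.8 = 150. Allocation 1:1 (6.6), so 60 evaluable or 75 recruited per arm.

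**Reproducing the stated figure.** For two equal arms of n, detectable d = (1.960 + 0.842) × √(2/n).

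- n = 120 per arm: 2.802 × 0.1291 = 0.3617, which rounds to the printed 0.362.
- n = 60 per arm: 2.802 × 0.1826 = 0.511 (0.516 with the t distribution).
- n = 75 per arm: 2.802 × 0.1633 = 0.457 (0.460 with t).

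In reverse, n per arm = 2 × 2.802² / 0.362² = 119.8, so 120 per arm (121 with t) and 240 evaluable in total.

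**Power at d = 0.362, unadjusted.** Power = Φ(0.362/√(2/n) − 1.960).

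| Per arm | Normal approximation | t distribution |
|---|---|---|
| 60 | Φ(1.983 − 1.960) = 50.9% | 50.3% |
| 75 | Φ(2.217 − 1.960) = 60.1% | 59.6% |
| 120 | Φ(2.804 − 1.960) = 80.1% | 79.8% |

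**Other readings tried with 60 per arm.** One-sided alpha 0.05 gives 63.2% power. The printed Z-beta of 0.8 gives a detectable d of (1.960 + 0.8) × 0.1826 = 0.504, so that rounding does not explain the gap. No reading tried gives 80% at d = 0.362 with 120 in total.

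**What the planned MMRM could add.** None of the following assumptions is in the protocol. Let r be the baseline to post-baseline correlation and ρ the between-visit correlation. Assume constant variance, complete data, and d scaled to the single-visit SD. To restore 80% with 60 per arm, the error variance must fall to (0.362/0.511)² = 0.50 of its unadjusted value.

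- *Week-24 contrast, baseline-adjusted:* the variance factor is 1 − r². Power is 55% at r = 0.3, 63% at 0.5 and 79% at 0.7. About r = √(1 − 0.50) = 0.71 is needed.
- *Average of the six post-baseline visits, baseline-adjusted:* V = (1 + 5ρ)/6 − r², and power = Φ(Δ/√(2V/60) − 1.960). If the effect is constant from week 4, Δ = 0.362. If it builds linearly to 0.362 at week 24, Δ = 0.362 × (1+2+3+4+5+6)/36 = 0.211.

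| r | ρ | V | Power, constant effect | Power, linear build-up |
|---|---|---|---|---|
| 0.3 | 0.3 | 0.327 | 93% | 53% |
| 0.5 | 0.5 | 0.333 | 93% | 52% |
| 0.7 | 0.7 | 0.260 | 97% | 62% |
| 0.3 | 0.5 | 0.493 | 81% | 38% |

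The planned contrast may therefore have well over 80% power or well under it, depending on assumptions that the protocol does not give.

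**The case against.** The strongest reply is that 50% is the power of an unadjusted comparison at one time point, which is not the planned test. Section 9.2 adjusts for baseline and averages over visits, and under favourable assumptions that model exceeds 90% power with 60 per arm. This stands. A reader might infer that the trial's real power is 50%, or that its primary test is no better than a coin toss. The protocol does not support that: it leaves the power of the primary contrast undetermined. But the reply does not rescue section 9.3, which invokes none of these gains and whose d matches the plain two-group formula for 120 per arm to three decimals.

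Four further inferences should be resisted.

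- That the word conservative is wrong. Section 9.3 uses it relative to the pilot, for which sections 2.1 and 2.5 report d = 1.19. Even 0.52 is less than half of that. Whether a schizophrenia pilot is a sound basis is a separate matter.
- That the N-acetylcysteine comparison fails at 0.52. Those effect sizes are not in the protocol, so this cannot be judged.
- That a null result would be taken to exclude effects of 0.36 or more. Section 9.2 commits to 95% confidence intervals, and they will show what is excluded.
- That the origin of the slip is known. A per-arm number used as a total would explain it, but section 9.3 shows no formula.

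**Conclusion.** The power statement in section 9.3 is wrong on its own inputs. With 60 evaluable per arm, an unadjusted two-sided comparison at 0.05 has about 50% power at d = 0.362, and reaches 80% at d of about 0.52. With 75 per arm the figures are about 60% and 0.46. These results rest only on the protocol's alpha, power, N, allocation ratio and attrition.

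The power of the planned MMRM is a separate quantity. Over the assumed correlations and time courses shown, it ranges from 38% to 97%, and the protocol gives no basis for choosing within that range. The finding is that the stated inputs do not yield 80%, not that the trial is known to be underpowered. It should be corrected because the figure is the stated basis for the sample size. The Z-beta of 0.8 is a minor rounding matter.

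**What to change.** Keep N as it is and revise section 9.3 in one of two ways.

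1. Restate the claim for the calculation actually done: 120 evaluable participants (60 per arm) give 80% power to detect d = 0.52 in an unadjusted two-group comparison at two-sided alpha 0.05.
2. Or state the assumed baseline correlation, between-visit correlation and time course of effect, and recompute power for the primary MMRM contrast. This is the more informative option if the sponsor wants credit for baseline adjustment and repeated measures.

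In either case, compare the earlier trial effects with the corrected threshold, and print Z-beta as 0.84. The description of the estimate as conservative relative to the pilot may stay.

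The cost is protocol wording, plus a short calculation under the second option. No participants, visits or procedures change. Under the first option the stated detectable effect becomes less favourable.

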10.1. Ethics review

All documentation pertaining to the study must be prepared in accordance with the requirements outlined by the relevant ethics committee. All documentation must then be approved or given a favourable opinion in writing by an HREC as appropriate.

The Coordinating Investigator along with the Trial Coordinator is responsible for informing the IRB or HREC of any amendment to the protocol in accordance with local requirements. In addition, the HREC must approve all advertising used to recruit participants for the study.

The study will be performed in accordance with ethical principles that have their origin in the Declaration of Helsinki and are consistent with ICH/Good Clinical Practice, applicable regulatory requirements. The NHMRC National Statement on Human Research will also be utilised.

